# 6.6.2.3. Rules for Duration of Exposure Prior to Start of Next Patient and Start of Next Cohort in Phase 1a

Dose escalation and accrual to the next cohort will occur only after the minimum number of patients required for tolerability assessment in the current cohort have completed Cycle 1, and only after acceptable tolerance has been demonstrated in at least 1 of 1, 3 of 3, or 5 of 6 patients treated in the current cohort (depending on cohort size), and after consultation with the Sponsor's Medical Monitor(s).

In cohorts with > 1 patient, enrollment will be staggered between the first and second patient by at minimum 24 hours in order to assess for IRRs; thereafter patients within a cohort may be added concurrently. For all patients, EOC1 assessments are to be performed no sooner than C1/D21 (-2 days).

#### 6.6.2.4. Rules for Establishing the Recommended Phase 2 Dose

The MTD (or a dose lower than the MTD) will be identified as the RP2D, provided a minimum of 6 patients have been treated at that dose, and provided acceptable tolerance has been demonstrated in at least 5 of 6 patients treated.

The RP2D choice will be based on the MTD evaluation as well as other toxicities observed in the study, including observations in later cycles of administration of AVID100, as well as on PK and other data.

#### 6.6.3 Phase 2a: Rules for Accrual

#### 6.6.3.1. Filling of Cohorts in Phase 2a

Once the MTD and/or RP2D have been identified, approximately 60 patients in 3 expansion cohorts will be enrolled to the Phase 2a portion of the study to more fully evaluate safety, tolerability, and the preliminary antineoplastic effect of study drug at that dose level.

Accrual to the Phase 2 Cohort may begin once the RP2D has been established and a minimum of 6 patients have been treated at that dose. If the Phase 1a MTD Cohort is to be expanded up to 12 patients to more fully evaluate safety and tolerability at that dose level, accrual to Phase 2a may begin concurrent with accrual of the additional up to 6 patients to that cohort.

### 6.6.3.2. Rules for Patient Population to be Treated in Phase 2a

Patients will be accrued to 3 expansion cohorts in the Phase 2a portion of the study. The tumor types to be evaluated in these expansion cohorts are mTNBC (~30 patients), SCCHN (~15 patients), and Sq-NSCLC (~15 patients).

Criteria for eligibility will be as described above with the additional requirement that patient tumors must have been documented to express EGFR by IHC\* in a central laboratory. Further, FFPE tumor tissue from either a prior procedure or a recent biopsy must be available for submission to a central laboratory for other study-related evaluations as planned per protocol.

\*\*DAKO EGFRpharmDX™IHC kit system technology to be utilized. For this study, EGFR-positive staining is defined as 3+ intensity in  $\geq 50\%$  of tumor cells or  $\geq 2+$  intensity in  $\geq 75\%$  of tumor cells for mTNBC; or 3+ intensity in  $\geq 50\%$  of tumor cells for SSCHN and Sq-NSCLC,, whether it is complete or incomplete circumferential staining.

### 6.6.3.3. Rules for Tolerability in Phase 2a

The criteria for tolerability during Phase 1a will apply to Phase 2a Expansion Cohorts. Safety will be reviewed on an ongoing basis to determine if the dose and schedule chosen based on the Phase 1a dose escalation is safe and well-tolerated in expanded populations of patients with the tumor types selected for the expansion cohorts (mTNBC, SCCHN, and Sq-NSCLC). Should it be determined that the dose is not well-tolerated (i.e.,  $\geq 33.3\%$  of patients in an expansion cohort experience a Cycle 1 DLT), the safety of that dose level will be re-evaluated and the next lower dose with established tolerability in Phase 1a will be administered to subsequent patients.

An exception will be the occurrence of toxicity suggesting organ damage (e.g., pulmonary fibrosis, drug-induced liver injury) occurring in  $\geq 2$  patients within an expanded cohort, in which case further accrual to that cohort will be discontinued.

# 6.7. Continued Therapy After Cycle 1

Upon completion of Cycle 1, in the absence of unacceptable toxicity or disease progression, patients may continue receive additional cycles of study drug Q3W ( $\pm$  2 days), unless further delay is required to allow for amelioration of toxicities. Administration of subsequent dosing cycles is allowable at the discretion of the Investigator, provided the patient meets the retreatment criteria listed below. Additional cycles should be initiated as soon as possible, but not longer than 2 weeks after the completion of the previous cycle, if feasible.

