	Criteria for eligibility will be as described above with the additional requirement that patient tumors must have been documented to express EGFR by IHC ( $3+$ intensity in $\geq$ 50% of tumor cells $\underline{or} \geq 2+$ intensity in $\geq$ 75% of tumor cells in mTNBC; $3+$ intensity in $\geq$ 50% of tumor cells in SCCHN and Sq-NSCLC) in a central laboratory. Further, FFPE tumor tissue from either a prior procedure or a recent biopsy must be available for submission to a central laboratory for other study-related evaluations.
	Rules for Tolerability The criteria for tolerability during Phase 1a will apply to Phase 2a Expansion Cohorts. Safety will be reviewed on an ongoing basis to determine if the dose and schedule chosen based on the Phase 1a dose escalation is safe and well-tolerated in expanded populations of patients with the tumor types selected for the expansion cohorts (mTNBC, SCCHN, and Sq-NSCLC). Should it be determined that the dose is not well-tolerated (i.e., ≥ 33.3% of patients in an expansion cohort experience a Cycle 1 DLT), the safety of that dose level will be re-evaluated and the next lower dose with established tolerability in Phase 1a will be administered to subsequent patients.
	An exception will be the occurrence of toxicity suggesting organ damage (e.g., pulmonary fibrosis, drug-induced liver injury) occurring in $\geq 2$ patients within an expanded cohort, in which case further accrual to that cohort will be discontinued.
Continued Therapy after Cycle 1	Upon completion of Cycle 1, in the absence of unacceptable toxicity or documented disease progression, patients may continue to be treated with study drug Q3W (± 2 days) unless

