#### **6.5.3.6.** Schedule

Study drug is to be administered once every 3 weeks (Q3W) on Day 1 of each cycle (3 weeks [21 days] equals 1 dosing cycle).

End of Cycle 1 (EOC1) assessments are to be performed no sooner than C1/D21 (-2 days). Subsequent cycles may be administered Q3W ( $\pm$  2 days), unless further delay is required to allow for amelioration of toxicities.

# 6.6. Cycle 1

A minimum of 1 cycle of AVID100 will be administered, if tolerated. Any interruptions in dosing and the reasons for such interruptions must be documented. If an AE is the cause for dosing interruption, it must be detailed on the Adverse Events page of the eCRF. Determinations regarding cohort escalation, DLTs, and MTD will be based on the toxicities observed during this 3 week period (Cycle 1) of treatment.

- Patients completing Cycle 1, in the absence of a DLT, will be considered to have tolerated the AVID100 regimen.
- Patients must receive their full planned dose of AVID100 during Cycle 1 in order to be considered evaluable for tolerability unless dose reduction, interruption, or discontinuation was the result of a DLT.
- Dose-Escalation Cohorts: Patients will be replaced, if necessary (e.g., received < 1 full dose of AVID100 plus follow-up through EOC1 [C1/D21 {-2 days]}]) for any reason other than a DLT), to allow for a thorough assessment of the tolerability in any dose cohort.

- All enrolled patients will be considered in the assessment of safety and tolerability.

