#### 6.6.2.2.1. Establishment of the MTD

- 1. Dose Part A: A minimum of 1 patient will be entered into dose Cohort 1 and 2 ONLY; the dose escalation between cohorts (until at most Cohort 3) will be 100%.
  - If during Cycle 1, a patient experiences a ≥ Grade 2 toxicity considered associated with study drug, the cohort will be expanded to 3 patients and Part B will commence.

- If during Cycle 1, a patient experiences a DLT considered associated with study drug, the cohort will be expanded to 6 patients and Part C will commence.
- 2. Dose Part B: A minimum of 3 patients will be entered into each dose cohort; the dose escalation between cohorts will be 50%.
  - If during Cycle 1, any 1 patient experiences a DLT considered associated with study drug, the cohort will be expanded to 6 patients and Part C will commence.
  - If during Cycle 1, > 1 patient experiences a DLT, dose escalation will STOP. This will indicate that the MTD has been exceeded.
- 3. Dose Part C: A minimum of 6 patients will be entered into any dose cohort where a DLT is observed in any of the first 3 patients, otherwise a minimum of 3 patients will be entered into each dose cohort; the dose escalation between cohorts will be 25%.
  - If during Cycle 1, > 1 patient experiences a DLT, dose escalation will STOP. This will indicate that the MTD has been exceeded.
- 4. If it is determined that a dose level is not tolerated, the previous lower dose cohort will be expanded to 6 patients (if this has not already been accomplished) as a total of 6 patients must be treated before establishing a dose as the MTD.
- 5. Once the MTD (or maximum dose to be studied) is achieved and the RP2D is identified, that cohort may be expanded up to 12 patients in order to more fully evaluate safety and tolerability at that dose level at the Sponsor's discretion.
- 6. Should the DLT rate equal or exceed 33.3%\* in an expanded MTD cohort, it will be determined that the dose is not tolerated. If this occurs, the previous lower dose cohort may be expanded as above. Therefore:
  - There is potential for expansion of lower dose cohort(s) if the initially identified MTD is not tolerated (either with single or repeat cycles of therapy), and
  - There is potential to evaluate and expand a previously unexamined intermediate dose level(s) between 2 established dose levels in order to more fully characterize tolerability.

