# 6.9. **Definition of Maximum Tolerated Dose**

The clinical endpoint of the Phase 1a portion of this trial is determination of the MTD of study drug that can be administered by the specified route, infusion duration, and schedule.

MTD will be defined as the dose below that which produces, during Cycle 1 of treatment, any of the indicated DLTs either in > 1 patient in a 3 to 6 patient cohort, or in  $\ge 33.3\%$ \* of patients in the event of an expanded 7 to 12 patient cohort.

\*i.e., > 2 DLTs when 7 to 9 patients have been treated.

The MTD will not be established until all patients entered into the cohort under evaluation have either completed Cycle 1 or discontinued further participation in the trial (or been dose-reduced) due to the occurrence of a DLT.

Previously established tolerability of a dose level will be reevaluated if DLTs thought to be possibly related, probably related, or related to study drug are observed in later cycles.

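### The Phase 2a tolerability rule gives two different actions for 1 DLT in a cohort's first 3 patients, and no minimum number of patients is stated before its percentage is read

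*Combined protocol and SAP*

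**What the plan says.** **Phase 2a rule.** Section 6.6.3.3 opens by importing the earlier rules: "The criteria for tolerability during Phase 1a will apply to" the Phase 2a expansion cohorts. It continues: "Safety will be reviewed on an ongoing basis to determine if the dose and schedule chosen" in Phase 1a holds up in the larger populations. It then defines a dose that is not well tolerated, in the synopsis wording, as "i.e., ≥ 33.3% of patients in an expansion cohort experience a Cycle 1 DLT". The consequence in 6.6.3.3 is that when 33.3% or more "of patients in an expansion cohort experience a Cycle 1 DLT), the safety of that dose level will be re-evaluated", with the next lower tolerated dose for patients treated afterwards. Section 3.3 (Filling of Cohorts) gives the same rule with a threshold of 33% or more.

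**Phase 1a rules.** Section 6.6.2.2.1, Part B: "If during Cycle 1, any 1 patient experiences a DLT considered associated with study drug, the cohort will be expanded to" 6 patients. Part C likewise takes a cohort to 6 when a DLT is seen in its first 3. Section 6.9 places the MTD below a dose producing "any of the indicated DLTs either in > 1 patient in a 3 to 6 patient cohort", or in 33.3% or more of an expanded cohort of 7 to 12. A footnote to 6.6.2.2.1 turns that percentage into counts: more than 2 of 7 to 9, and more than 3 of 10 to 12.

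**Timing and size.** Phase 2a safety calls are monthly (6.10). The only pause tied to a patient count is at 15 per mTNBC subgroup, and it is for activity (3.3). Planned cohorts are about 30, 15 and 15 (6.6.3.2).

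**Denominator.** Section 6.6 states "All enrolled patients will be considered in the assessment of safety and tolerability", but also requires the full Cycle 1 dose for a patient to be evaluable for tolerability. Follow-up for evaluability is 3 weeks in 9.2 and 2 weeks in 14.3.1.

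**The concern.** For one early data set, 1 DLT in 3 patients, the same paragraph supports two actions. The imported Phase 1a criteria say to treat more patients before judging the dose. The percentage says the dose is not well tolerated and that subsequent patients get a lower one. Since no starting number is given, the percentage can be read from the first patient.

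The rule sets the dose in cohorts whose primary objective covers both safety and antineoplastic effect (3.2.1). If two sites or two safety calls read it differently, the dose in a cohort depends on the reading. A change part-way would also leave the first-15-patient response rate used for the decisions in 14.2 mixed across doses. That second consequence follows from the design but has not been sized here.

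**Working it through.** **1. Reproduce the plan's own counts.** The smallest number of DLTs k with k/n at or above 33.3%, set against the Phase 1a counts (6.9 and the 6.6.2.2.1 footnote):

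| Patients n | Smallest k by percentage | Phase 1a count for not tolerated |
|---|---|---|
| 1 or 2 | 1 (100% or 50%) | none stated for a Part B or C cohort |
| 3 | 1 (33.33%) | 2 |
| 4 to 6 | 2 | 2 |
| 7 to 9 | 3 | 3 |
| 10 to 12 | 4 | 4 |
| 13 to 15 | 5 | none stated |
| 16 to 30 | 6 rising to 10 | none stated |

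The footnote's counts reproduce. The two rules disagree at n = 3; at n = 1 or 2 the percentage is met by a single event where Phase 1a has no matching count. Using the 33% of section 3.3 in place of 33.3% changes no entry.

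**2. Chance of the disputed data.** With true Cycle 1 DLT rate p, P(at least 1 DLT in 3) = 1 − (1 − p)³.

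- p = 5%: 1 − 0.95³ = 14.3%
- p = 10%: 1 − 0.90³ = 27.1%
- p = 20%: 1 − 0.80³ = 48.8%

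For comparison, P(2 or more in 3) at 10% is 2.8% and at 20% is 10.4%. The values of p are assumptions, because the documents state no DLT rate for Phase 2a.

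**3. Chance that a cohort ever triggers.** An exact binomial recursion adds one patient at a time, moves the probability at or above the boundary into the triggered total, and carries the rest forward.

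- Literal percentage: trigger when DLTs ≥ n/3 (rounded up), checked after every patient.
- Phase 1a counts: trigger at 2 or more among the first 6, then at one third or more.

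| True DLT rate | Literal, 15 patients | Phase 1a counts, 15 patients | Literal, 30 patients | Phase 1a counts, 30 patients |
|---|---|---|---|---|
| 5% | 15.0% | 3.5% | 15.0% | 3.5% |
| 10% | 29.9% | 12.9% | 30.0% | 13.0% |
| 20% | 58.3% | 42.0% | 59.6% | 44.0% |

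At 10%, 27.1 of the 29.9 percentage points come from a DLT among the first 3 patients.

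**4. Any of the three cohorts at 10%,** treating cohorts of 15, 15 and 30 as independent:

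- Literal: 1 − (1 − 0.299)² × (1 − 0.300) = 66%.
- Phase 1a counts: 1 − (1 − 0.129)² × (1 − 0.130) = 34%.

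**5. Sensitivity to the starting number** (15 patients, 10% rate, then checked after every patient):

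| First look at n | P(trigger) |
|---|---|
| 1 or 3 | 29.9% |
| 4 or 6 | 12.9% |
| 7 | 6.0% |
| 10 | 2.8% |
| 15 | 1.3% |

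Starting at 3 instead of 1 changes nothing, so the result does not rest on acting at 1 of 1 or 1 of 2. Starting at 4 or 6 gives the same value as the Phase 1a counts.

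**The case against.** The strongest reply is that a coherent reading exists. For an expanded Phase 1a cohort the criterion is itself a DLT rate at or above 33.3%, with counts from 7 patients. Phase 2a opens only after at least 6 patients have been treated at the RP2D (6.6.3.1), and section 2.6 reports no Cycle 1 DLT among the 6 evaluated. On that reading 6.6.3.3 imports the expanded-cohort rule and lacks only a starting number. This is plausible, and it correctly limits the conflict to early accrual. But 6.6.3.3 does not say which Phase 1a criterion it imports, and its percentage is taken within an expansion cohort, which excludes the Phase 1a patients from the denominator.

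A second reply is that a formal decision after every patient is unlikely. DLT status takes a 3-week cycle, roughly 6 to 12 centres enrol, calls are monthly, and a Study Safety Committee exercises judgement. Several patients may be dosed before the first formal reading. So the literal figures are an upper case for frequency of review. Judgement does not remove the conflict: the determination is defined numerically, and the dose consequence is worded as certain.

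Third, part of early accrual has passed. The footnote to the Phase 2a adverse event table counts 13 patients at 15 April 2020, and the table marks an event as a DLT. A reader might infer that the trigger was met and ignored. The documents do not support that: the cohort and cycle of the event are not visible in the available text.

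The denominator matters less than it may appear. Patients with a DLT count either way; only incompletely treated or followed patients without a DLT differ.

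**Conclusion.** The concern holds as an early-accrual conflict. Section 6.6.3.3 and the synopsis give opposing actions for 1 DLT in 3 patients, and no minimum number is stated. The like-for-like effect at an assumed 10% rate is 29.9% against 12.9% per 15-patient cohort, about 2.3-fold, and 66% against 34% for any of three cohorts. These figures assume a constant DLT rate, independent patients and cohorts, and a check after every patient.

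Two stronger readings do not stand. One is that the Phase 2a trigger contradicts the Phase 1a counts in general: from 4 to 12 patients they agree exactly. The other sets 29.9% against the 1.3% from a single look at 15 patients and claims a gap of more than 20-fold. A single look at cohort end does not fit ongoing review or a dose change for subsequent patients.

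Two smaller gaps remain: the integer counts stop at 12 although cohorts are 15, 15 and 30, and the threshold is written two ways. This should be corrected because a stated dose rule yields conflicting actions. It does not show that the chosen dose is unsafe or that either rule is the right one.

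**What to change.** - Reconcile section 6.6.3.3, section 3.3 and the synopsis with the Phase 1a counts they invoke, so that 1 DLT in 3 has one stated consequence, and write the threshold the same way throughout.
- State the number of evaluable patients from which the percentage is first read, and when it is read again.
- Extend the integer counts of the 6.6.2.2.1 footnote to 15 and 30 patients.
- Name one denominator: all treated or evaluable patients, with one follow-up length (9.2 and 14.3.1 differ), and whether mTNBC is one cohort of 30 or two of 15, since Appendix I treats it as two.

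The boundary and the action attached to it are for the sponsor's clinical and safety team. The cost is a wording amendment to a few paragraphs. A short table of trigger probabilities for the chosen rule would help that team but is optional.

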#### **6.7.1** Retreatment Guidelines

Clinical judgment will be used when determining whether it is advisable to continue a patient on to the next cycle(s) of dosing. In order to start any new cycle a patient must meet the following criteria:

- ANC  $\geq$  1,000 per mm^3
- Platelets  $\geq 75,000 \text{ per mm}^3$
- Any ongoing AEs should NOT meet the criteria for DLT.
- Any ongoing AEs should have either ameliorated to ≤ Grade 1 severity, returned to baseline status, or resolved, with the exceptions of Grade 2 alopecia, clinical events that are being adequately controlled with best supportive care (e.g., nausea, vomiting, diarrhea, fatigue), and asymptomatic laboratory abnormalities that are considered clinically insignificant or that are resolving with medical therapy.

Should any one of the criteria above not be met, dosing of study drug must be delayed.

### 6.7.2 Doses and Regimens

For a given patient, subsequent cycles of therapy with AVID100 will be administered at the same dose and infusion duration established for that patient during Cycle 1, and on the same schedule, unless dose reduction is necessary (or a dose adjustment is necessary due to  $\pm$  10% [less at the site's discretion or if required by institution procedures] fluctuation in patient weight).

#### 6.7.3 Evaluation Schedules

The same evaluations required during Cycle 1 of the study will be conducted during subsequent cycles, at the frequencies indicated (see **Section 7**; Study Assessments).

#### **6.7.4 Duration of Treatment**

Additional cycles of AVID100 may continue to be administered if tolerated and in the absence of documented disease progression, at the Investigator's discretion, provided retreatment criteria have been met (see Section 6.7.1; Retreatment Guidelines).

Such extended therapy will continue for a period of up to 12 months after achieving the "best response," at which time the Medical Monitor and Investigator will discuss the advisability of continued therapy based upon the patient's ongoing response status and the degree of demonstrated tolerability.

### 6.7.5 Retreatment Following a Response

Treatment with AVID100 may be restarted in a patient who:

- Previously achieved a documented OR on this study, stopped treatment, and subsequently progresses, or
- Discontinued therapy for a reason other than a DLT or PD, and in whom documented OR or prolonged SD is subsequently noted.

Such action may be taken at the Investigator's discretion, following discussion with the Medical Monitor, provided retreatment criteria are met, no anti-cancer treatment was administered since the last dose of AVID100, and the trial is still open. This option for retreatment does not apply to patients who previously experienced an unacceptable toxicity that required permanent discontinuation of study drug (see **Section 9.1 #1**; Criteria for Treatment Discontinuation).

Retreatment with AVID100 may be initiated at the same dose and infusion duration established for that patient during their previous course of treatment, and on the same schedule, unless dose reduction is necessary.

The same evaluations required during previous treatment will be conducted during subsequent cycles, at the frequencies indicated.

Retreatment cycles of AVID100 may continue to be administered if tolerated and in the absence of further disease progression, at the Investigator's discretion, as long as retreatment criteria continue to be met.

# 6.8. Toxicity and Dose Limiting Toxicity

# **6.8.1** Toxicity Grading

The CTCAE Version 5.0\*) will be used to grade AEs occurring during this study.

\*See < https://ctep.cancer.gov/protocolDevelopment/electronic applications/ctc.htm >

